9.4 Process evaluation

In order to understand how our interventions were implemented and received by participants, we will conduct a mixed-methods process evaluation.³⁵ All participants will be asked to complete an end-of-study fixed response questionnaire measuring their satisfaction with the wearable device, research technology platform, and intervention design. They will also complete a series of validated surveys including MOS Social Support Survey,¹⁸ and the EQ-5D health-related quality of life survey.¹⁹⁻²¹ to explore changes in participant characteristics associated with strong or poor performance. All questionnaires and surveys will be administered electronically via the Way to Health portal.

We will conduct semi-structured qualitative interviews with study participants purposefully selected by performance. In each arm, we will split the participants into two groups based on performance above and below the mean of that arm. We will randomly invite up to 10 participants from each of the two groups to complete a 30-minute telephone interview (up to 80 total participants across all 4 arms, or until we reach saturation in each group). We will provide \$50 for participating in the interview.

Interviews will be conducted by a trained research assistant using a semi-structured interview guide informed by the theoretical domains framework (TDF).^{36,37} The TDF provides a lens through which to view the cognitive, affective, social and environmental influences on behavior in relation to the implementation of complex interventions to improve health.³⁸ It includes 14 domains: knowledge, skills, social role and identity, beliefs about capabilities, optimism, reinforcement, intentions, goals, decision processes, environmental context and resources, social influences, emotion and behavioral regulation. We will create open-ended interview questions informed by these domains. The guide will also include questions on the following topics: (1) factors motivating participation in the study, (2) prior experiences with trying to increase physical activity, (3) perceptions of the intervention including its impact on his or her performance and perceived risks and benefits. Participants will be asked to describe aspects of each intervention element that helped them to achieve their physical activity goals and aspects that did not. The interview guide will also elicit information about intervention burden as well as suggestions for improvement in intervention design. The interview guide will be developed, refined and piloted prior to the trial launching.

Interviews will be audio recorded and professionally transcribed. Transcripts will be uploaded to qualitative data analysis software (e.g. NVivo) for management and coding. Two trained coders will perform the coding, in close collaboration with the study PIs. We will utilize a mixed inductive-deductive

approach to analysis.³⁹ We will begin by reading through a subset of transcripts from respondents in both performance levels to generate our preliminary coding framework. We will create two types of codes in this phase of analysis: (1) descriptive codes based on our interview guide and factors previously identified in the literature and (2) interpretive codes that emerge from the data.

Once the coding framework has been created and discussed with the study team, the coders will read through the interview transcripts line by line and apply codes to the data. The coding framework will be open to expansion and refinement throughout analysis, should the coders come upon novel salient themes. Intercoder reliability will be assessed every fifth transcript. We will calculate a coefficient of reliability (the ratio of coding agreements to the total number of coding decisions) for one selected interview document.⁴⁰ A coefficient of greater than 0.95 will be our cut off for proceeding with the coding. If our coefficient is less than 0.95, we will review the discrepancies, refine code definitions and reeducate the coders to ensure reliability. Once the entire data set has been coded, we will perform cross-code searches and explore variation in themes across respondents by performance on the intervention and by sociodemographic characteristics to identify higher-order patterns.

9.5 Safety analysis

Participants will be asked to report any study-related injuries or hospitalizations. These will be reviewed with the Principal Investigator and the patient will be contacted if there is a risk to continuing in the trial. We will constitute a DSMB comprised of 3 experts with one being a statistical expert, another an expert in physical activity, and a third being someone who is experienced in leading trials of behavioral interventions. As per NIH guidelines we are not naming anyone now so as not to preclude reviewers from their academic institutions. All adverse events will be reported to the IRB and DSMB. We will also ask participants to report study-related injuries, falls, emergency department visits, and hospitalization on the 12-month and 18-month surveys. We will evaluate these data in a blinded fashion after 25%, 50%, 75%, and 100% of participants complete the intervention and follow-up periods. This plan will be reviewed with the DSMB and modified as necessary prior to participant enrollment. Our plan will be to have milestone-driven meetings with the DSMB likely approximately every six months.

References

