goals (goal gradients)³⁷ and uses loss aversion to help motivate ongoing efforts to not lose status. Each participant begins the intervention in the silver level. By starting them in the middle, the higher levels seem within reach and they will feel a sense of loss from dropping down a level in the first week if they don't achieve 40 points; this may motivate them to initiate greater activity. Every 8 weeks, we will reach out to individuals that are stuck in lower levels of blue or bronze and restart them back at silver. This allows for another "fresh start" and creates a new endowment effect as someone who is already at the bottom would otherwise not be able to drop down further and experience loss aversion. At the same time, we will also inquire if he or she would like to adjust their step goal as long as they are within the range of a 33% to 50% increase. In previous studies, we've found that some individuals set overly ambitious goals at the start of the intervention and that for participants who have trouble achieving their initial goals, we can re-engage them if goals are reset to a more reasonable level.

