5.4 Accrual

We will enroll and randomize 1050 participants over a two-year period.

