5.6 Key exclusion criteria

Participants will be excluded if they: 1) are already participating in another physical activity study; 2) an 18-month physical activity program is infeasible (e.g. metastatic cancer; unable to ambulate or provide informed consent) or unsafe (currently pregnant or told by a physician not to exercise); 3) they do not have a device (e.g. smartphone, tablet, or computer) to transmit data from the wearable activity tracker; 4) baseline step count is 7,500 or greater; 5) they do not have a primary care physician in the University of Pennsylvania Health System.

6. Subject recruitment

Participants will be recruited from the University of Pennsylvania Health System (UPHS) which consists of five large hospitals including the Hospital of the University of Pennsylvania, Penn Presbyterian Medical Center, Pennsylvania Hospital, Chester County Hospital, and Lancaster General Hospital. There are more than 60 primary care practice clinics affiliated with UPHS throughout Pennsylvania and New Jersey. Target population: The UPHS population includes patients of mixed socioeconomic status with a high rate of ASCVD. Based on initial evaluation, there are more than 100,000 patients at UPHS who meet criteria for with a 10-year ASCVD $\geq 7.5\%$ or clinical ASCVD. This will provide an ample population from which to perform the proposed clinical trial given that we typically are able to recruit about 30% of eligible health system patients for our studies and the target sample size is 1,050 or about 1% of the eligible population.

Potentially eligible patients will be identified using data from the electronic health record and Penn Data Store, the health system's clinical data warehouse. They will be invited to participate either by e-mail or mail letters. Study coordinators will conduct follow-up phone calls to further assess interest and answer questions related to the study. In the initial invitation, patients will have the ability to opt out from any further communications. Interested patients will be instructed to visit the study website on the Way to Health research technology platform to learn more about the study, create an account, provide informed consent, and complete initial baseline and eligibility surveys.

7. Subject compensation

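### Harms are found only by participant self-report: death is not listed, and no route is described for events in participants who drop out or do not respond

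*Combined protocol and SAP*

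**What the plan says.** Section 9.5 of the combined protocol and SAP gives two ways in which harms reach the study team. The first is ongoing: "Participants will be asked to report any study-related injuries or hospitalizations". The second is scheduled: "We will also ask participants to report study-related injuries, falls, emergency department visits, and hospitalization on the 12-month and 18-month surveys". Both depend on the participant. The ongoing request is limited to events the participant takes to be related to the study. In the survey item the same qualifier attaches at least to injuries, and the sentence leaves open whether it covers the rest of the list.

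The section also states: "All adverse events will be reported to the IRB and DSMB". That fixes where events go once known. It does not say how they come to be known. The data are then reviewed periodically: "We will evaluate these data in a blinded fashion after 25%, 50%, 75%, and 100% of participants complete the intervention and follow-up periods".

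Death is not named as a safety event. No section describes record review, a vital-status check, contact with a relative, or follow-up of non-responders for safety. The table in section 8.2 collects cardiovascular history, weight and medications at 6, 12 and 18 months, again by survey.

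Two other places bear on the remedy. Section 6 says: "Potentially eligible patients will be identified using data from the electronic health record and Penn Data Store". The fifth exclusion in section 5.6 removes people if "they do not have a primary care physician in the University of Pennsylvania Health System".

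**The concern.** The population has raised ASCVD risk or existing ASCVD, and each participant is followed for 18 months while being encouraged to walk more. Some deaths, cardiac admissions and injuries should be expected whatever the effect of the interventions. Self-report is weakest for the most serious of these. A participant who dies reports nothing. One who stops because of an injury or admission may be less likely than others to complete a later survey. The relatedness qualifier adds a further filter: a participant may leave out a cardiac admission because it seemed unconnected with the study.

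At stake is what the DSMB sees at its planned reviews, and any later statement on safety. Both would rest on participants who survived and answered, and the plan gives no means of telling how many events lie outside that group.

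**Working it through.** The plan states no figure for harms, so there is none to reproduce. The check has two parts.

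**1. Can either described source record the event?**

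| Event | Ongoing report (9.5) | 12- and 18-month surveys (9.5) | Other described source |
|---|---|---|---|
| Death | No | No | None |
| Event before dropout | Only if the participant reports it as study-related | Only if a later survey is completed | None |
| Event after dropout or in a non-responder | Only if the participant still volunteers it | No | None |
| Event in a responder | Yes, if judged study-related | Yes, subject to recall and the qualifier | 8.2 cardiovascular history, by survey |

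The first row needs no assumption. The second and third depend on how many participants stop reporting.

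**2. How large could the loss be?**

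Inputs from the plan: 1050 randomised (section 5.4); 150 in control and 300 in each intervention arm (section 9.1); 10% dropout (section 9.1). The 10% was set for the power calculation and is used here only as a proxy for the fraction giving no report.

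Participants without a report: 0.10 × 1050 = 105, made up of 0.10 × 150 = 15 in control and 0.10 × 300 = 30 in each of the three intervention arms (15 + 3 × 30 = 105).

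Let d be the fraction giving no report and RR the event risk in non-reporters divided by that in reporters. The share of all events unseen is

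d × RR / (d × RR + 1 − d).

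At d = 0.10:
- RR = 1: 0.10 / (0.10 + 0.90) = 10%
- RR = 2: 0.20 / (0.20 + 0.90) = 18%
- RR = 3: 0.30 / (0.30 + 0.90) = 25%

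The documents give no RR, so these three values are assumptions. Varying d, also by assumption:

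| d | RR = 1 | RR = 2 | RR = 3 |
|---|---|---|---|
| 0.05 | 5% | 9.5% | 14% |
| 0.10 | 10% | 18% | 25% |
| 0.20 | 20% | 33% | 43% |

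The formula treats every event in a non-reporter as lost. Some would be reported before dropout, or at month 12 by someone who misses only month 18, so each entry is an upper figure for its d and RR. It also treats responders' reports as complete, which errs the other way.

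**The case against.** The best defence is that this is a step-goal behavioural trial with safety oversight in proportion. Safety is not a primary, secondary or exploratory outcome (section 3). A DSMB receives all adverse events, and the plan is to be reviewed with it and changed as needed before enrolment. Payments for assessments rise from $30 at month 6 to $40 at month 12 and $50 at month 18 (section 7), which works against non-response. The survey questions and payments do not differ by arm. All of this stands. It lowers the likely loss, but none of it names a source for deaths or for events in non-responders.

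A reader might infer three stronger points that the documents do not support.

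- *Detection differs by arm.* Section 5.1 gives the gamification arm, and so also the combined arm, an extra contact: "Every 8 weeks, we will reach out to individuals that are stuck in lower levels of blue or bronze and restart them back at silver". Supportive sponsors are contacted as well. More incidental reports from these arms are possible. But the outreach covers only participants in the two lowest levels, its stated purpose is to restart levels and revisit step and support goals, and nothing says that harms are asked about. A difference is not shown.
- *A planned safety comparison is biased.* Section 9.5 describes blinded review and specifies no comparison between arms.
- *The health-system record would find every event.* A primary care physician in the system does not mean that emergency care, admission or death occurs there, and the documents do not say that the record holds deaths or outside care.

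**Conclusion.** The gap is real. Section 9.5 relies on self-report alone, omits death, and describes no route to events in people who drop out or do not respond. That rests on the text and needs no assumption. 'No described route' is the right wording: staff may learn of some events informally.

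The size is illustrative. With 10% giving no report, about 105 participants are affected and 10% to 25% of events go unseen as the risk ratio runs from 1 to 3. A reader might take 25% as the expected loss; it is the upper end of an assumed range, and equal risk gives 10%. No count of deaths is offered, because the documents give no mortality rate.

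This is an improvement that should be made to a stated method, not an internal contradiction. It leaves the primary analysis untouched.

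**What to change.** In section 9.5:

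1. Add death to the listed harms.
2. Add a query of the health-system record and Penn Data Store for deaths, emergency department visits and hospitalizations in all randomised participants, from randomisation to month 18, whatever their survey or device status. Run it before each planned safety review.
3. Keep the 12- and 18-month surveys, since the record holds in-system events only and will not show a fall that led to no medical contact.
4. Show record-based and self-reported events separately. If serious events are ever tabulated by arm, use the record-based source, which does not depend on how often staff are in touch with a participant.

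The cost is a repeated query of a source the trial already uses for recruitment. Consent wording may also be needed if current authorisation does not cover outcome data; the consent pages are not in the public document, so this cannot be checked. Care and deaths outside the system would still be missed.

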5.2 Study duration

This study is anticipated to take up to 5 years to complete. Each participant will be enrolled in a 12-month intervention and 6-month follow-up period.

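### Add the injury, fall, emergency-visit and hospitalization questions to the paid 6-month survey: unscheduled reporting and DSMB oversight exist, but no harms question is scheduled in a participant's first 12 months

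*Combined protocol and SAP*

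**What the plan says.** Section 9.5 describes several layers of safety oversight.

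- **Unscheduled reporting.** "Participants will be asked to report any study-related injuries or hospitalizations". These reports are reviewed with the Principal Investigator. No schedule is given.
- **Onward reporting.** "All adverse events will be reported to the IRB and DSMB".
- **Scheduled questions.** "We will also ask participants to report study-related injuries, falls, emergency department visits, and hospitalization on the 12-month and 18-month surveys".
- **Aggregate evaluation.** "We will evaluate these data in a blinded fashion after 25%, 50%, 75%, and 100% of participants complete the intervention and follow-up periods".
- **DSMB meetings.** The plan is for "milestone-driven meetings with the DSMB likely approximately every six months". Neither the first meeting date nor the material to be reviewed is stated.
- **Room to change.** "This plan will be reviewed with the DSMB and modified as necessary prior to participant enrollment".

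Section 7 pays all participants for a 6-month assessment. The Section 8.2 table lists six survey areas at that visit, including an item on cardiovascular history, weight and medication. Section 5.2 sets the time on study: "Each participant will be enrolled in a 12-month intervention and 6-month follow-up period". Section 5.4 sets accrual: "We will enroll and randomize 1050 participants over a two-year period".

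**The concern.** The trial already contacts and pays everyone at 6 months, but Section 9.5 does not use that contact to ask about harms. A participant is first due a specific harms question a full year after starting. Until then, capture depends on the participant volunteering a report, and the general request names only injuries and hospitalizations. Falls and emergency visits are named only for the later surveys.

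Three things are at stake. Events in the first months must be volunteered or recalled up to 12 months later. Someone who leaves before month 12, possibly because of an injury, may never be asked. And the aggregate evaluation, the only one with a stated trigger, is tied to completion, so under most accrual patterns it comes when most or all of the sample is already randomized.

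**Working it through.** The plan gives no calendar month for its safety looks, so there is no stated figure to reproduce. Months below count from first randomization, and survey dates are counted from each participant's randomization.

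**Inputs**

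- 1,050 participants over 24 months (Section 5.4); no accrual pattern is given.
- 12 + 6 = 18 months per participant (Section 5.2).
- First completion-based look at 25% of participants (Section 9.5): 0.25 × 1,050 = 262.5.
- Dropout of 10% (Section 9.1), used only for sensitivity.

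**Step 1: floors that need no accrual assumption.** The earliest anyone can finish both periods is 0 + 18 = month 18. If finishing the intervention alone counted, it is 0 + 12 = month 12.

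**Step 2: even accrual (assumed).** A fraction f is randomized by month 24f.

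- Both periods complete, 24f + 18: months 24, 30, 36 and 42 for f = 0.25, 0.50, 0.75 and 1.
- Intervention only, 24f + 12: months 18, 24, 30 and 36.
- Randomized by the first look: all 1,050 at month 24, or 1,050 × 18/24 = 787.5 (about 788) at month 18.
- If the 25% must be completers out of 1,050 after 10% dropout: (0.25/0.9) × 24 + 18 = month 24.7, or 18.7 on the intervention-only reading.

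**Step 3: scheduled harms responses due by month 12.**

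- Current plan: these are 12-month responses, so they equal the number randomized by month 0, which is 0.
- With 6-month items: the number randomized by month 6, which is 1,050 × 6/24 = 262.5 (about 262).
- If the full 10% dropout had already occurred: 262.5 × 0.9 = 236.

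By month 18 under even accrual, about 262 participants are due a harms response under the current plan. With 6-month items it is 1,050 × 12/24 = 525.

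**Step 4: range over other assumed accrual patterns.**

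| Assumed accrual | 25% randomized | First look, both periods | First look, intervention only | 6-month responses due by month 12 |
|---|---|---|---|---|
| Even | month 6 | month 24 (1,050 randomized) | month 18 (about 788) | about 262 |
| Half in months 0–6, half in 6–24 | month 3 | month 21 (about 963) | month 15 (about 788) | 525 |
| One third in months 0–12, two thirds in 12–24 | month 9 | month 27 (1,050) | month 21 (875) | 175 |

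Under every pattern the current plan has 0 scheduled harms responses due by month 12.

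**Step 5: do the DSMB meetings fill the gap?** Under even accrual the completion looks are themselves six months apart. The milestone-driven meetings could therefore be those same looks, or could be additional and earlier. The text does not settle which. In either case a meeting does not create a scheduled question to participants.

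**The case against.** The strongest reply is that oversight is layered and still provisional. Individual reports go to the Principal Investigator, all adverse events go to the IRB and DSMB, and a DSMB that meets about every six months could review accumulating events well before month 24. The plan is to be revisited with the DSMB before enrollment. Section 5.6 also excludes people for whom the program is unsafe or whom a physician has told not to exercise. All of this stands. A reader might infer that safety monitoring is absent until month 24, or that the DSMB sees nothing before then. The documents do not support that: what the meetings will review is unstated, which is not evidence that earlier review will not happen.

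A second reply is that the content of the 6-month survey is only partly visible. The cardiovascular history item may catch some events, and the Section 8.2 table shows no harms row at 12 or 18 months either, so its silence at 6 months proves nothing. This is right. The point rests on the sentence in Section 9.5 that names the two later surveys. None of the areas listed at 6 months names injuries, falls or emergency visits.

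Two other inferences should be resisted. One is that the 8-week ramp-up is the period of greatest hazard. Section 5.1 describes it as a gradual rise toward the target, so goals are highest after it ends, and no period of peak risk is shown. The other is that early data would reveal a difference between arms. Split 1:2:2:2, 262.5 responses are about 37 in control and 75 in each intervention arm, too few for that purpose.

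**Conclusion.** The point holds as an inexpensive improvement to a stated schedule. It is not an error or contradiction in the plan, and it does not touch the primary analysis. What the documents establish without further assumption is that Section 9.5 schedules no harms question before a participant's month 12, and that its completion-based evaluation cannot begin before trial month 18 (12 on the more generous reading). The month-24 and month-18 dates and the figure of about 262 depend on even accrual. Under the other patterns tried, the first look ranges over months 21 to 27 (15 to 21 on the generous reading) and the added responses over 175 to 525. Because unscheduled reporting and DSMB oversight exist, the benefit is limited to timeliness, shorter recall, reaching some participants before they drop out, and earlier overall harms rates.

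**What to change.** 1. Add the same injury, fall, emergency-visit and hospitalization items to the existing 6-month survey in all arms. Amend Section 9.5 accordingly, and show the items at 6, 12 and 18 months in the Section 8.2 table.
2. State that the roughly six-monthly DSMB meetings already planned will receive a cumulative safety summary that includes these responses. Keep the 25%, 50%, 75% and 100% completion looks as they are.

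Both changes can be settled at the DSMB review that the plan already schedules before enrollment. The cost is protocol wording, a little more participant time on a survey already given and paid for, and earlier preparation of tables.

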Once baseline measures have been established, participants will be contacted to choose their goals using an approach we have found to work well in previous studies. They will be given their baseline step count and asked to select a step goal increase of 33%, 40%, 50% or choose a custom goal as long as it is at least 1500 steps greater than baseline. We have used this approach in the past because it gives participants the options of setting their own goal but also steers people to choose one of the options provided, any of which would be terrific from the standpoint of increasing physical activity. Leaving it completely open-ended risks having participants either pick goals that are ‘too easy’ or not likely to be attainable. In prior work, we find that on average participants chose ambitious goals and more than half selected a 50% step increase.

--Randomization—

Participants that have established baseline measures and finished goal selection will be randomly assigned to control or one of the three interventions using a 1:2:2:2 allocation and stratifying on baseline step count (< 4000 steps, 4000 – 7000 steps, > 7000 steps) using an electronic number generator through the Way to Health research technology platform. We do this because it preferentially increases power for comparison between the different intervention arms, as the differences between intervention arms are likely to be smaller than the difference between the intervention arms and control.

--Study Arms—

All participants will be asked to use the wearable device during the day and at night to measure activity. Each participant will primarily receive study communications by text message. Interventions by study arm will vary as follows:

--Arm 1: Control—

During the intervention and follow-up periods, participants in this arm will receive a daily text message stating whether or not they achieved their step goal on the prior day.

--Arm 2: Gamification intervention—

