9.1 Power and sample size

Physical activity has been demonstrated to have a direct dose relationship with reduction in the risk of cardiovascular disease and events, with even small increases significantly lowering risk.^{6,22-25} We use 1000 steps as our threshold for powering statistical significance, which for the average person is about half a mile and takes about 10 minutes of MVPA.²⁶ Based on our prior work,¹⁰⁻¹⁴ we estimate a standard deviation in the primary outcome of 2500 steps. This study has been powered for six comparisons

between arms using a common cutoff for the test statistics that ensures the familywise error rate is at most 0.05. This is the approach suggested in Follmann et al.²⁷ and it generalized Tukey's Honest Significant Differences approach for an unbalanced design. We estimate that a sample of 1050 participants allocated in a 1:2:2:2 distribution (150 in control and 300 in each intervention arm), will ensure 93% power to detect a 1000 step difference between each intervention arm and control, with a standard deviation of 2500 steps and an 8-minute difference in MVPA assuming a standard deviation of 20 minutes. This calculation assumes a 10% dropout rate. We estimate that we will have at least 85% power to detect a 750-step difference with a standard deviation of 2500 steps and a 6-minute difference in MVPA with a standard deviation of 20 minutes.

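### Section 9.5 does not define its blinded safety evaluations, and no comparison of harms by arm is planned at any time; if the data are pooled, an excess in one arm is diluted

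*Combined protocol and SAP*

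**What the plan says.** Section 9.5 (Safety analysis) is the only section on harms. Its elements are:

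- **Data.** "We will also ask participants to report study-related injuries, falls, emergency department visits, and hospitalization on the 12-month and 18-month surveys".
- **Periodic evaluation.** "We will evaluate these data in a blinded fashion after 25%, 50%, 75%, and 100% of participants complete the intervention and follow-up periods". The evaluator is not named beyond the pronoun, and blinded is not defined.
- **Case review.** Of reported injuries and hospitalizations: "These will be reviewed with the Principal Investigator and the patient will be contacted if there is a risk to continuing in the trial".
- **DSMB.** Three members, one of them a statistical expert. "All adverse events will be reported to the IRB and DSMB". "Our plan will be to have milestone-driven meetings with the DSMB likely approximately every six months". "This plan will be reviewed with the DSMB and modified as necessary prior to participant enrollment".

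Section 9.5 gives no expected event rate, no table by arm, no between-arm comparison and no condition for unmasking. Section 9.2 (Comparative-effectiveness analysis) models physical activity outcomes only, so it does not supply the missing comparison.

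The arm sizes come from Section 5.1, where participants are "randomly assigned to control or one of the three interventions using a 1:2:2:2 allocation", and from Section 9.1, which gives a "1:2:2:2 distribution (150 in control and 300 in each intervention arm").

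**The concern.** In a randomized trial the informative safety question is whether an intervention raises the rate of injuries, falls, emergency visits or admissions above control. Here even the evaluation at 100% is blinded and no end-of-trial safety comparison is described. A team that followed the plan to the letter would never ask that question.

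Case-by-case review cannot replace it. Participants have a 10-year ASCVD risk of at least 7.5% or existing ASCVD, so some falls and admissions will occur in every arm, and a single event cannot be attributed to an arm's intervention. Only rates by arm can show an excess.

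If blinded means pooled, each evaluation can only compare one overall rate with an expected rate, and the plan states none.

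**Working it through.** The safety section has no rate, boundary or power figure to reproduce. The one plan figure used is the allocation: 1050 × 1/7 = 150 in control and 1050 × 2/7 = 300 in each intervention arm, as Section 9.1 states.

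**Step 1: dilution if pooled.** Let the background risk be p and the relative risk in one intervention arm be RR. The pooled rate is p × (5/7 + RR × 2/7).

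- RR = 2: 5/7 + 4/7 = 9/7, a ratio of 1.29.
- RR = 3: 5/7 + 6/7 = 11/7, a ratio of 1.57.

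Only 2/7 of the excess is visible.

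**Step 2: an illustration at the 50% look.** The documents give no event rates, so p and RR are assumptions. I take RR = 2 in one arm and p = 5%, 10% and 20%. At 525 participants the arms hold 75 / 150 / 150 / 150. For p = 10% the expected pooled count is 7.5 + 15 + 15 + 30 = 67.5, against 10% × 525 = 52.5 with no excess (12.9% versus 10%).

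Four ways of looking are compared. The two by-arm tests are two-proportion z-tests with cutoff 1.96. The pooled tests ask whether the total exceeds the upper 97.5% binomial limit for the presumed background. At p = 10% that limit is about 52.5 + 1.96 × √(525 × 0.10 × 0.90) ≈ 66 events. If 12% is thought normal it is about 63 + 1.96 × √(525 × 0.12 × 0.88) ≈ 78 events, well above the 67.5 expected.

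Probability of flagging the doubling:

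| View at the 50% look | p = 5% | p = 10% | p = 20% |
|---|---|---|---|
| Affected arm vs other three combined | 55% | 85% | >99% |
| Affected arm vs control | 23% | 49% | 87% |
| Pooled, background known exactly | 30% | 55% | 88% |
| Pooled, background thought to be 1.2 times the true one | 4% | 8% | 14% |

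The pooled view depends on knowing the background. An error of one fifth in that rate removes most of its ability to detect the excess.

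**Step 3: where the by-arm view is weak.** Arm versus control rests on 75 control participants at this look and does no better than pooled data with a perfectly known background. None of the by-arm figures allows for multiplicity: for p = 10%, a Bonferroni correction for three intervention arms lowers 85% to about 73%, and for three arms at four looks to about 58%.

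**Step 4: harm shared by two arms.** Arm 4 combines both interventions, so harm from one component could appear in two arms. With p = 10% doubled in two arms, arm 4 versus the rest flags about 40%, and at least one affected arm is flagged at most about 73% of the time. Pooled data against an exactly known 10% flag about 98%. The ranking in Step 2 is therefore not general.

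**Step 5: timing.** Assume uniform accrual over the two years in Section 5.4, 18 months per person, and looks counted at completion of both periods. The 25% look then falls at 6 + 18 = 24 months, when those enrolled after month 12, about half, are still in intervention. The 50% look falls at 12 + 18 = 30 months, with about a quarter left. The 75% look falls at 18 + 18 = 36 months, when the last intervention period ends. Only the first two looks can inform the care of people still in intervention.

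**The case against.** The strongest reply is that Section 9.5 never says the data are pooled. A blinded evaluation can be split by masked arm codes, and then nothing is diluted. The sentence is written in the study team's voice, so it may mean only that the investigators stay unaware of arm, which is good practice: some of these items are self-reported and need a judgement of relatedness to the study. The section also has real safeguards: every adverse event goes to the DSMB, it meets about every six months, and it reviews the plan before anyone is enrolled.

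Much of this stands. A reader might infer that the DSMB is masked, that the data are pooled, and that an arm-specific harm will stay hidden until the final analysis. The documents support none of these as fact. The text does not mention masking of the DSMB, does not use the language of pooling, and does not describe a final safety analysis in which the harm would emerge. A reader might also take the 85% for one arm against the other three as the gain from splitting the data. It is not the comparison with control, which gives 49% in the same scenario.

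The reply does not remove the gap. None of the safeguards promises rates by arm with denominators. The pre-enrollment review is an opportunity to specify them, not evidence that they are specified. Under every reading of blinded, a comparison of harms by arm is absent from the plan.

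**Conclusion.** The point holds in conditional form. What the documents establish is that blinded is undefined, that the evaluator is not clearly named, and that no tabulation or comparison of harms by arm is planned during or after the trial. What follows only if the data are pooled is dilution: a doubled risk in one 300-person arm shows as a 1.29-fold overall rise, with no reference rate to set it against.

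The detection figures illustrate the size of the effect under assumed event rates and do not predict what this trial would see. They show that by-arm tables usually help when one arm carries the harm, that they do not guarantee detection because control is small, and that pooled data can do better when two arms share the harm and the background is truly known. This is a cheap improvement to the safety plan, not a flaw that threatens the trial's main result.

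**What to change.** Amend Section 9.5, and the DSMB's working documents to match, as follows:

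1. Define blinded and name who performs each evaluation.
2. At each of the four planned evaluations, give the DSMB a closed table of injuries, falls, emergency visits and hospitalizations by arm, coded or unmasked, with denominators or person-time. If codes are used, note that the 1:2:2:2 sizes will identify control.
3. Keep efficacy data out of that table, so that no alpha is spent, and let the investigators see pooled data only.
4. Add an end-of-trial tabulation of harms by arm.

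The cost is a few sentences and the same tables split by one more variable, with no added sample size or participant burden. There are two small downsides. Someone who already has data access must hold the arm codes apart from the investigators. Early by-arm counts will also be noisy: at the 25% look control has about 37 participants and each intervention arm about 75, so the DSMB should read them with that in mind.
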